6.9 Study Duration

The study duration for all enrolled subjects in this trial is approximately 12.5 months, including a 2-week Screening Phase for enrollment following initiation of consent documentation, 12 months of follow-up after treatment in the Active Phase, and an optional long term follow up period of an additional 24 months. Study enrollment is anticipated to require approximately 3-6 months. Therefore, the total study duration will be approximately 39.5 – 42.5 months. Subjects who have unremitting pain, or worsening conditions and who had been randomized to

CONFIDENTIAL	Clinical Protocol	DATE	P	age
		9Dec2019		1
TITLE: V iable A llograft S upplemented Disc Regeneration in the T reatment of		WRITER	NO.	REV
Patients with Low Back Pain wit	th or without Intervertebral Disc Herniation –	TG, DB, PW	28	6
VAST-001-017				

the conservative group will be evaluated clinically and be given the option to crossover into the allograft supplement group. All randomized subjects will have the option to receive the allograft treatment during the optional long term follow up at 24 months. These subjects will fill out questionnaires at 36 months and have the opportunity to do so over the phone.

This study may be terminated by the sponsor if deemed necessary and documented by an amendment to this protocol. If the study is terminated, the sponsor will support follow-up of those subjects who entered the study as though the study had not been terminated.

6.10 Subject Withdrawal and Replacement

Subjects may withdraw from the study at any time without penalty and for any reason without prejudice to their future medical care. In all cases, the reason(s) for withdrawal, and the primary reason, must be recorded on the appropriate case report form (CRF). If a subject is prematurely withdrawn from the study after randomization (Day 0 of the Active Phase), the investigator must document the reason(s) and make every effort to perform a final Termination Visit. The procedures to be followed for the Termination Visit are the same as those defined for the Month 12 Visit.

Subjects that are consented, screened and randomized, but do not undergo a successful transplantation (Day 0 of the Active Phase) will be considered screen failures. These randomization assignments will be re-used. The randomization and the replacement of subjects will be orchestrated through a 3rd party designated independent of the data collection or analysis.

CONFIDENTIAL	Clinical Protocol	DATE	Р	age
		9Dec2019		
Patients with Low Back Pain with	mented Disc Regeneration in the $\underline{\mathbf{T}}$ reatment of th or without Intervertebral Disc Herniation –	WRITER TG, DB, PW	NO. 29	REV 6
VAST-001-017				

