6.2 Patient Identification and Randomization

The Informed Consent Form (ICF), signed prior to any study specific screening procedures being completed, will provide details on both the Screening Phase and the Active Phase of the study. Each patient that signs Informed Consent will be randomized to the active allograft, placebo, or conservative care treatment group. The randomization will occur through a secured envelope system, during which the subject will be provided with a unique subject identification number (XX-XXX, site number-subject number). During the Screening Phase, all subjects randomized to active allograft or placebo treatment will be scheduled for a transplantation procedure, while the conservative care treatment subjects will be followed as per the routine standard of care.

CONFIDENTIAL	Clinical Protocol	DATE	Р	age
		9Dec2019		
Patients with Low Back Pain with	mented Disc Regeneration in the $\underline{\mathbf{T}}$ reatment of the or without Intervertebral Disc Herniation –	WRITER TG, DB, PW	NO. 26	REV 6
VAST-001-017				

On or before Day 0 of the Active Phase, the patency of the affected disc will be confirmed, and subjects determined eligible from the screening phase who have consented to participation and are randomized to allograft treatment will receive the study material. Patients are considered enrolled in the study when they undergo successful treatment in the Active Phase and receive either allograft treatment, placebo (saline) treatment, or conservative care treatment.

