6.3 Blinding

The assignment to treatment (active allograft, or placebo, or conservative care) is open label at Day 0 of the Active Phase to the extent that subjects receiving allograft or placebo will not be aware of what they have received, while those assigned to conservative care will be aware. All site study staff will be aware of the group to which each subject is randomized. Sites will be trained to ensure that subjects receiving the allograft or placebo treatment will remain blinded to their treatment throughout the study duration. Subjects will be unblinded during the study exit or upon signing of the new informed consent for the study extension.

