8.4.1 Transplant of supplemental allograft into the affected disc

All subjects randomized to active allograft will undergo an intervertebral lumbar injection into the target disc. The procedure of injecting the intervertebral disc will involve placing a 22-gauge needle into the center of the affected intervertebral disc. No contrast will be used prior to the injection of the supplemental allograft and 1mL of cells (approximately 6*10⁶ cells) mixed in a 1:1:0.75 by-volume ratio (Cells in cryoprotectant: Saline: NP) will be injected into the center of the affected disc(s) in the location of the nucleus pulposus. At least 1.5-2 milliliters of the resulting mixture will be available for injection into the nucleus pulposus of the symptomatic disc. Volume injected will be recorded.

Vital signs will be recorded prior to injection. The treatment injection should be carefully controlled. The injection procedure MUST be stopped if any of the following occur:

- The investigator cannot accurately place the needle tip in the nucleus pulposus
- The subject becomes hemo-dynamically unstable during the injection procedure.

CONFIDENTIAL	Clinical Protocol	DATE	P	age
		9Dec2019		T
TITLE: V iable A llograft S upplemented Disc Regeneration in the T reatment of		WRITER	NO.	REV
Patients with Low Back Pain wit	th or without Intervertebral Disc Herniation –	TG, DB, PW	36	6
VAST-001-017				

The following information regarding the treatment procedure must be documented:

- Procedure start and stop time
- Treatment administration stop time
- Treatment interruption information, if applicable
- Total volume of treatment injected
- Pain on implantation
- Anesthesia type(s)

The information collected above will also be collected during the placebo cross over visit.

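### Section 6.10 puts an assignment that site staff have already seen back into use and does not say how it is concealed again

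*Protocol*

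**What the plan says.** Protocol 6.10 deals with subjects who have been consented, screened and randomised. Those who "do not undergo a successful transplantation (Day 0 of the Active Phase) will be considered screen failures". It continues: "These randomization assignments will be re-used". The next sentence is the only safeguard offered: "The randomization and the replacement of subjects will be orchestrated through a 3rd party designated independent of the data collection or analysis".

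Protocol 6.3 blinds patients in the two injected arms but not the sites: "All site study staff will be aware of the group to which each subject is randomized".

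Protocol 6.2 gives the mechanism, "The randomization will occur through a secured envelope system, during which the subject will be provided with a unique subject identification number". That number is made up of a site number and a subject number. The same section randomises at consent: "Each patient that signs Informed Consent will be randomized to the active allograft, placebo, or conservative care treatment group". Section 8.5 puts randomisation after eligibility has been confirmed, and Appendix A puts it at VA1 (Day 0).

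The SAP mentions neither re-use of assignments nor replacement of subjects.

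**The concern.** Concealment requires that whoever decides whether and when a patient enters cannot know that patient's arm. A returned assignment fails this wherever the site can tell that it is the next one to be issued. Staff could then choose, delay or pass over a patient to suit the slot.

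The slots at risk are allograft and saline, because only those arms have a transplantation that can fail. That is the one comparison in which patients are blinded, and both co-primary endpoints are patient-reported. Bias at entry would undo much of what the saline arm is there to provide.

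The point is separate from how failed subjects are analysed. Keeping them in the ITT set would not conceal their replacements' allocation.

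**Working it through.** **1. The passages side by side.**
- The assignment is issued and the site knows it (6.2, 6.3).
- The subject then has no successful transplantation. This can happen because the procedure is halted (8.4.1: "The injection procedure MUST be stopped if any of the following occur"). It can also happen because the subject never reaches injection, for instance through non-compliance during screening (6.8). The earlier randomisation takes place, the longer this window is.
- The same assignment becomes available again (6.10).
- No passage says that it is re-concealed, shuffled, moved to another site or withheld from the next patient.

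**2. The plan's own figures.**
- Ratio 3.5:1:1 on 220: 220 × 3.5/5.5 = 140 and 220 × 1/5.5 = 40, as stated. The shares are 63.6%, 18.2% and 18.2%.
- Measurement error (Protocol 13.3, SAP 4): 15.5 × √(1 − 0.75) = 7.75, as stated.

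**3. What foreknowledge adds.** With an unopened assignment and no small blocks, the best guess (allograft) is right 63.6% of the time. For a returned assignment issued next at the same site, the guess is right 100% of the time. With equal failure rates, 140/180 = 77.8% of returned slots are allograft and 22.2% are saline.

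**4. How many.** Let f be the share of injection-arm assignments that fail. The documents do not give f, so 1% to 15% is assumed. Expected re-uses are k = 180f/(1 − f), and their share of all randomisations is k/(220 + k). The fraction of injected subjects who entered through a returned slot is f.

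**5. Worst-case bias.** Assume that every slot returns to the same site. Staff place patients whose 12-month change is 7.75 points better into known allograft slots and 7.75 points worse into known saline slots. The bias is 2 × f × 7.75. The 7.75 is only a convenient size (half an SD); the plan says nothing about how far staff could steer. For scale, the standard error of the contrast is 15.5 × √(1/140 + 1/40) = 2.78.

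| f | Re-uses k | Share of randomisations | Bias (ODI points) |
|---|---|---|---|
| 1% | 1.8 | 0.8% | 0.2 |
| 5% | 9.5 | 4.1% | 0.8 |
| 10% | 20.0 | 8.3% | 1.6 |
| 15% | 31.8 | 12.6% | 2.3 |

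**6. Effect on the planned tests.** This was simulated with normal data, SD 15.5 and 140/40/40, for one endpoint. The test is Kruskal-Wallis at 5%, then Dwass-Steel-Critchlow-Fligner (pairwise |z| above 3.314/√2 = 2.344).

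| f | False allograft v saline claim | Overall Kruskal-Wallis rejection |
|---|---|---|
| 0 | 1.7% | 5% |
| 5% | 2.1% | 5.5% |
| 10% | 3.3% | 7.2% |
| 15% | 6.0% | 10.7% |

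A separate run of 40,000 trials per setting applied the 7.75-point shift only to a random fraction f of subjects in each injected arm. For f = 0, 5, 10 and 15% it gave 1.8%, 2.0%, 3.4% and 5.3% for the pairwise claim, and 5.3%, 5.5%, 7.2% and 9.9% overall. At f = 1% neither rate moved beyond simulation error.

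**The case against.** The strongest reply is that disclosure does harm only if the site also knows when and where the slot comes back. Section 6.10 gives replacement to an independent third party, who could return the assignment to an unpredictable place in a central list. That is correct, and the effect would then be close to zero. But 6.10 says who runs replacement, not how a seen assignment becomes unknown again, and its independence is from data collection and analysis. The gap remains.

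Three stronger readings are tempting, and the documents do not support them.
- A reader might infer that the next allocation at the site *is* known. That needs site-held envelopes and next-patient re-use. A site prefix on a subject number does not establish a site-specific list, and no order of re-use is stated. Foreknowledge is possible, not shown.
- A reader might infer that a re-used slot can never be conservative care. The trigger, no successful transplantation, makes sense only for the injected arms. However, 6.2 counts conservative care as a treatment that must be received for enrolment, and 6.10 is silent on a conservative-care subject lost before Day 0.
- A reader might compute type I error for a stand-alone 140 v 40 comparison at an unadjusted 5%, and get 5.9%, 8.6% and 13.3% at f = 5, 10 and 15%. That is not the planned test. The gated, adjusted procedure gives the smaller pairwise figures above. Requiring both co-primaries can only lower the success rate further.

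The inputs are also stacked: f has no source in the documents, and steering is assumed on every slot and in opposite directions by arm.

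**Conclusion.** The concern holds as a fault in a stated rule, and not merely as a missing detail. The protocol re-uses assignments that unblinded staff have seen, and nothing in either document restores concealment. Whether any allocation would actually be foreknown depends on operational details that are not given.

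At an assumed f of 1% to 15%, about 2 to 32 assignments (0.8% to 13% of randomisations) are exposed. The worst-case bias is 0.2 to 2.3 ODI points. On one endpoint, false allograft v saline claims would rise from about 1.7% to about 2%, 3% and 5–6% at f = 5, 10 and 15%. Overall Kruskal-Wallis error would rise from 5% to about 5.5%, 7% and 10–11%. At 1% to 2% failure there are only about 2 to 4 such slots (180 × 0.02/0.98 = 3.7) and little follows. The rule should be changed because it can bias the key contrast and is cheap to remove; the documents do not show that bias has occurred.

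**What to change.** In Protocol 6.10, replace the re-use sentence with: *A randomisation assignment is never re-used; a replacement subject receives the next unused, concealed assignment, released by the third party only after eligibility is confirmed and the subject is registered.* Align 6.2, 8.5 and Appendix A on when randomisation takes place. Keep any block structure out of the protocol, since unblinded sites read it and could deduce late assignments in a block.

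The cost is a few lines of wording and final arm sizes that may differ from 140/40/40 by a few subjects. The third party is already in place.

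Randomisation may already be complete: the synopsis refers to patients who took part in the trial, and SAP section 13 describes imaging as collected. In that case:
- have the third party list every re-used assignment with its site, arm and next recipient, and report the count;
- add to the SAP a sensitivity analysis of both co-primary endpoints that excludes subjects who entered through a re-used assignment.

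That analysis would drop about 180f subjects: 1.8 at f = 1% and 27 at f = 15%.

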7 EFFICACY AND SAFETY MEASUREMENTS

7.1 Study Procedure

In the scope of routine procedures of the investigating centers, each patient with the given indication will undergo treatment as defined in the study. Besides the investigator's standard of care procedure, after being informed about and giving consent to the screening for potential participation in the study, the following evaluations will be performed for each patient.

7.1.1 Screening Phase Day -14 to Day 0 or VS1:

Potential subjects will be identified and will provide written informed consent for the entire study before undergoing screening and study specific procedures. The investigator or designee will check the inclusion and exclusion criteria and collect the patient data and medical history. A physical examination will be performed and all concomitant diseases and medication will be documented. The scores/scales defined as ODI, VASPI, and SF-36 will be completed by the subject, and assisted by the physician or physician designate (as needed), and a "baseline" MRI, X-ray, and laboratory evaluation will be performed. All required assessments are outlined in Appendix A. VS1 may require multiple clinic visits during this 14-day eligibility screening period. Patients will have had disc pain for a minimum of 6 months to be included. Ineligible subjects should be identified early in the process and prior to completing an MRI and X-ray. MRI and X-ray images up to 6 months prior to treatment are acceptable.

7.1.2 Active Phase Day 0 or VA1:

The Baseline Visit (Day 0) of the Active Phase will occur for subjects that are consented and meet eligibility criteria. MRI/X-ray images performed up to 6 months prior to Day 0 are acceptable to be used for eligibility criteria assessment. Subjects who continue to meet all inclusion and exclusion criteria will need to have all baseline questionnaires, scores/scales, and additional assessments completed, including concomitant diseases, medication information and resource utilization as outlined in Appendix A. All subjects randomized to the allograft or placebo treatment groups will have the patency of the affected disc confirmed. Hereafter, these subjects will undergo preparation for receiving the supplemental allograft treatment or randomized to placebo treatment (saline), or randomized to conservative care treatment.

CONFIDENTIAL	Clinical Protocol	DATE	P	age
	nented Disc Regeneration in the T reatment of n or without Intervertebral Disc Herniation –	9Dec2019 WRITER TG, DB, PW	NO. 30	REV 6

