6.4 Treatments administered

Subjects screened and eligible for the Active Phase of the study will have diagnosis of the affected disc to normal standard procedures for all treatment groups. At the baseline visit (Day 0) of the Active Phase, eligible subjects who are randomized into allograft or placebo treatment will undergo a transplantation procedure. This procedure will consist of the following:

- 1. Transplant supplemental viable allograft into the affected disc
- 2. Transplant placebo saline treatment as alternative arm of study.

These procedures are outlined in detail in Appendices B and C respectively.

At 24-months, placebo saline subjects and active allograft subjects are eligible to receive the allograft injection.

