8 INCLUSION / EXCLUSION CRITERIA

8.1 Inclusion Criteria

Patients will be entered into this study only if they meet ALL of the following criteria:

- Able to provide an English written Informed Consent
- Age 18 to 60 years inclusive
- Male or female
- Body mass index <35
- Pfirrmann Grade [3-6]
- Radiographic confirmation by MRI/X-ray of:
 - (1) translational instability defined as ≤5 mm, or
 - (2) angular instability defined as ≤5°
- Back pain (with or without radicular leg pain) measured by:
 - (3) ODI of at least 40%, and
 - (4) VASPI of at least 40mm
- Pathologic level between L1 and S1
- 1 or 2 vertebral level involvement that has been evaluated for at least 6 months and treated with conservative care
- Symptomatic back pain attributable to intervertebral disc for a minimum of 6 months
- No previous surgical treatment at the disc level(s) being considered
- Psychosocially, mentally and physically able to fully comply with this protocol, and follow-up schedule
- Ability to undergo allograft transplantation
- Life expectancy >2 years
- No contraindications to MRI
- No history of malignancy (basal cell carcinoma) or chronic infectious disease (e.g. HIV, Hepatitis)
- Agree to use appropriate contraception; not planning on becoming pregnant for 24 months after treatment
- Patient disc for transplant confirmed by inter-discal pressure measurement, or disc-imaging study.
- No signs or symptoms of infection
- No chronic use (>7 consecutive days) of anticoagulants (such as aspirin) or NSAIDs prior to treatment

CONFIDENTIAL	Clinical Protocol	DATE	P	age
		9Dec2019		
	mented Disc Regeneration in the $\underline{\mathbf{T}}$ reatment of th or without Intervertebral Disc Herniation –	WRITER TG, DB, PW	NO. 34	REV 6

8.2 Exclusion criteria:

- Seropositive or seronegative spondyloarthropathy
- Type III Modic changes
- Prior surgeries of segments between L1 and S1
- Chemonucleolysis or percutaneous laserectomy of the affected disc prior to the study
- Chronic facet syndrome
- Stenosis of the spinal canal that is moderate to severe or more in degree
- Spondylodiscitis
- Spondylolisthesis (lysis and degenerative)
- Severe motor deficit or cauda equina disorder based on investigator determination
- Congenital abnormalities of the spinal nerves
- Pelvic and inguinal angiopathy
- Neurogenic inguinal syndrome
- Syringomyelia
- Diastenomatomyelia
- Traumatic neurological disorders
- Diseases of the kidney (nephritis, pyelonephritis)

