8.5 Assessments

- Informed Consent will be obtained between Screening Day -14 and Active Day 0, prior to any study procedures being performed. The addendum for optional long term follow up will be collected before procedure and questionnaires are performed.
- An assessment of eligibility using the inclusion and exclusion criteria will be conducted starting at Day -14 of the Screening Phase. Prior to randomization at Day 0 of the Screening Phase, eligible subjects must meet all inclusion criteria and no exclusion criteria for the Active Phase. This will also be assessed after the ICF addendum for long term follow up is collected to determine if the subject is still eligible.
- Medical History and Patient Demographics will be recorded during the Screening Phase.
- An abbreviated Physical Examination will be done in the Screening Phase within the 2 weeks prior to transplant, as well as at Month 6, and 12, and at 3 months for the subjects randomized to continue conservative care. This will be done for subjects completing the placebo crossover injection as well.
- Resource utilization data (lost time from work, number and kind of previous surgeries, duration of complaints (preoperatively), duration of rehabilitation, complications, additional physician visits, etc.), will be obtained during the Screening Phase as a baseline to similar data obtained during the Active Phase at Months 6, and 12. This will also be collected during the long term follow up visits of 24 and 36 months.
- Physicians clinical assessments will be collected in the Screening and in the 2 weeks prior to transplant, and in the Active Phase at Months 6, and 12, and in the conservative

CONFIDENTIAL	Clinical Protocol	DATE	Р	age
		9Dec2019		
	mented Disc Regeneration in the $\underline{\mathbf{T}}$ reatment of th or without Intervertebral Disc Herniation –	WRITER TG, DB, PW	NO. 37	REV 6

- care patients at 3, 6, and 12 months. A neurological exam will be completed before placebo crossover additionally.
- Patient self-assessments including VASPI, ODI, and SF-36 will be collected at every scheduled clinic visit. VASPI, ODI, and SF-36 will be collected in person at 24 months and at the 36 month interval, these questionnaires can be performed over the phone during optional long term follow up.

CONFIDENTIAL	Clinical Protocol	DATE	Р	age
		9Dec2019		

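### The protocol contradicts itself on when, and in which arms, disc eligibility is settled, so subjects can be removed from the injected arms after allocation with no matching step in conservative care

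*Protocol*

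**What the plan says.** Section 8.1 of the protocol sets the entry rule: "Patients will be entered into this study only if they meet ALL of the following criteria". One item on the list is "Patient disc for transplant confirmed by inter-discal pressure measurement, or disc-imaging study". It carries no arm restriction, although it is worded in terms of transplant. Section 8.5 sets the order: "Prior to randomization at Day 0 of the Screening Phase, eligible subjects must meet all inclusion criteria".

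Other sections put it differently. Section 6.2 has each consenting patient randomised, with no eligibility condition in that sentence, and then says: "On or before Day 0 of the Active Phase, the patency of the affected disc will be confirmed". That clause names no arm. Section 7.1.2, describing the Day 0 visit, names two: "All subjects randomized to the allograft or placebo treatment groups will have the patency of the affected disc confirmed". Section 6.4 says that subjects "will have diagnosis of the affected disc to normal standard procedures for all treatment groups".

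Two further rules matter. Section 6.10 classes randomised subjects who do not have a successful transplantation as screen failures and returns their assignments for re-use. SAP section 6.2 limits the primary efficacy population (mITT) to subjects who were treated and have a post-treatment ODI and VASPI.

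**The concern.** The only disc check that the protocol describes as a step at the treatment visit falls, in section 7.1.2, after allocation and only in the two injected arms. A subject who fails it and is not injected can be relabelled a screen failure, replaced, and left out of the mITT set. A comparable subject in conservative care meets no such step and stays in the analysis. Section 6.3 says that site staff know every subject's allocation, so the check is also made with the arm known.

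Conservative care is one of the three groups in the primary tests of ODI and VASPI (SAP section 9.1). If disc status is related to 12-month change, part of any difference from conservative care would reflect who was left in the analysis rather than treatment. Allograft and saline face the same check, so this asymmetry does not affect the comparison between them.

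**Working it through.** **Passages side by side**

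| Place | When disc status is settled | In whom |
|---|---|---|
| Protocol 8.1 | Before entry | Every patient |
| Protocol 8.5 | Before randomisation | Every patient |
| Protocol 6.2 | Randomisation follows consent; patency by Day 0 at the latest | Arm not stated |
| Protocol 6.4 | Diagnosis of the disc; timing not tied to randomisation | All arms |
| Protocol 7.1.2 | Day 0 visit | Already randomised to allograft or saline |
| Appendix A | Eligibility at VS1; eligibility re-check and randomisation both at VA1, order not shown; no row for disc confirmation | Not split by arm |

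Sections 8.1 and 8.5 agree with each other. Sections 6.2 and 7.1.2 do not fit with them, and Appendix A does not settle the order. No section defines patency or links it to the criterion in 8.1.

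**How a failed check reaches the primary analysis**

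1. A subject randomised to allograft or saline fails the Day 0 check and is not injected.
2. Under Protocol 6.10 the subject becomes a screen failure and the assignment is re-used.
3. Under SAP 6.2 the subject is not in the mITT set, having had no treatment.
4. In conservative care step 1 has no counterpart, so steps 2 and 3 do not follow.

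**Illustration of size**

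The plan gives no figure on this point. Two of its planning inputs serve for scale: a 9-point difference and an SD of 15.5 (Protocol 13.3, SAP 4). They reproduce the plan's own probability: Φ(−9 / (15.5 × √2)) = 0.3407, stated as 0.341.

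Two inputs are not in the documents and are assumed: the share f who would fail the check (5% to 20%), and the difference d in 12-month ODI change between those who fail and those who pass (5 to 10 points).

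Let subjects who pass have mean change m and those who fail m + d. With no treatment effect, the injected arms after removal have mean m, and conservative care has m + f × d. The spurious difference is f × d in size, with the sign set by the unknown sign of d.

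- f = 5%, d = 5: 0.05 × 5 = 0.25 points, or 3% of 9
- f = 10%, d = 10: 0.10 × 10 = 1.0 point, or 11% of 9
- f = 20%, d = 10: 0.20 × 10 = 2.0 points, or 22% of 9

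Subjects who would fail but remain in conservative care: 40 × f = 2 to 8. To fill 180 treated places (140 + 40) under re-use, 180 / (1 − f) = 190 to 225 subjects would be randomised to injection, so 10 to 45 would be dropped.

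For allograft v conservative care, SE = 15.5 × √(1/140 + 1/40) = 2.78. By a normal approximation, the unadjusted two-sided rejection rate under no effect rises from 5% to 5.1% at 0.25 points, 6.5% at 1.0 and 11.1% at 2.0. This is on the mean scale; the planned test uses ranks.

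The documents do not bound these ranges. With f near zero the bias is near zero; f = 30% and d = 15 would give 4.5 points.

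**The case against.** The case on the other side is substantial.

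- **Every arm is bound by the criterion.** Sections 8.1 and 8.5 exempt no one, section 6.4 provides disc diagnosis in all arms, and the eligibility rows in Appendix A are not split by arm. Section 7.1.2 itself opens by limiting Day 0 to subjects who meet the eligibility criteria.
- **Imaging can satisfy it.** The criterion accepts a disc-imaging study, every patient has a screening MRI, and section 7.1.2 adds: "MRI/X-ray images performed up to 6 months prior to Day 0 are acceptable to be used for eligibility criteria assessment".
- **Patency may be something else.** A check made just before injection can be a procedural step that has no meaning in an uninjected arm.
- **Timing and arms are not firmly fixed.** Section 6.2 allows the check before Day 0, and the sentence that follows the one quoted from 7.1.2 is garbled enough to be read as check first, allocation to any arm afterwards.
- **No section says that failing patency removes a subject.** The conditions for stopping the injection in section 8.4.1 do not mention it.

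Most of this stands. A reader might infer that conservative care is never held to the disc criterion, or that the arms have different entry rules. The documents do not support that: the rule nominally binds all three arms, and screening imaging could meet it in each. Treating patency as the 8.1 criterion is also an inference. Section 4.3 gives it some support, since the pilot study used a pressure measurement to show that the disc would retain the transplant, but it is not a definition.

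The objections do not remove the core. If the two checks are the same, the sections conflict on timing and arm. If they differ, an undefined check after allocation can still lead, through section 6.10 and the mITT definition, to exclusions in two arms only.

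**Conclusion.** The concern holds in a limited form. The protocol is inconsistent on when and in whom disc eligibility is settled, and its replacement rule combined with the treated-only mITT set opens a route for arm-dependent exclusion after randomisation. That can bias comparisons with conservative care, and through them the three-group test.

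Neither size nor direction can be derived from the documents. The 0.25 to 2 points depend on assumed f and d, on subjects who fail the check going uninjected, and on disc status being related to outcome.

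A reader might also infer that the bias would persist under intention-to-treat. It would not: if every randomised subject, including those who fail the check, is analysed in the assigned arm, all arms retain them and this source of bias is zero. The SAP's ITT label does not guarantee this, because SAP section 6.1 defines the set by enrolment with eligibility confirmed, and subjects reclassified as screen failures may be missing from it.

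**What to change.** 1. Reconcile Protocol 6.2, 6.4, 6.10, 7.1.2, 8.1 and 8.5 so that they give one sequence, and define patency.
2. Document the disc-confirmation criterion for every patient before the randomisation envelope is opened, by the imaging route that the criterion already allows and the screening MRI that every patient has.
3. State that any patency check at Day 0 is procedural and is not an eligibility decision. Whether a disc that fails it is injected is a clinical matter outside this point.
4. Keep subjects who fail that check in the analysis as randomised. Do not label them screen failures or re-use their assignments, and adjust the treatment condition in SAP section 6.2 so that it does not remove them.

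The cost is wording and the reordering of an existing screening step, with no new procedure if imaging is used. Some patients would fail screening earlier, and a few uninjected subjects would stay in the injected arms' analysis, which may dilute the estimated effect slightly.
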